#### 1.4. Study Rationale

Aberrant activation of PI3K $\delta$  has been associated with increased malignant B-cell proliferation and survival. Another PI3K $\delta$  inhibitor, idelalisib, received approval from the FDA for the treatment of patients with relapsed CLL, in combination with rituximab, and also received accelerated approval from the FDA for the treatment of patients with relapsed follicular B-cell non-Hodgkin lymphoma (FL) or relapsed small lymphocytic lymphoma. Idelalisib was also approved by the European Medicines Agency for patients with chronic CLL who have received at least 1 prior therapy or in certain first-line settings and for FL that is refractory to at least 2 lines of treatment. The approvals were based on objective response rate (ORR) and demonstrate that inhibition of PI3K $\delta$  can be an effective strategy in the treatment of some B-cell malignancies.

INCB050465 is a potent and selective inhibitor of PI3K $\delta$  in enzyme and B-cell proliferation assays. Based on emerging safety, efficacy, [REDACTED] data from the ongoing Study INCB 50465-101 (see Section 1.3), subjects with relapsed or refractory DLBCL who have received 2 to 5 prior regimens and who are ineligible for HDC/ASCT will receive INCB050465 administered orally at a dose of 20 mg QD for 8 weeks followed by 20 mg once weekly. This dose was chosen based on emerging efficacy and safety data from the ongoing Study INCB 50465-101 (see Section 1.3). [REDACTED]

Furthermore, 20 mg QD has demonstrated efficacy in DLBCL (2 CMRs in 2 subjects) and in other types of non-Hodgkin lymphomas (9 objective responses in 9 subjects with non-Hodgkin lymphoma). However, 24% (n = 11) of all subjects in study INCB 50465-101 discontinued study treatment due to an AE. All but 1 of these events occurred after the 9-week disease assessment. Among the subjects with an objective response (n = 20), 7 (35%) discontinued study treatment due to an AE. Consequently, after administration of 20 mg QD for 8 weeks, the dosing regimen will be reduced to 20 mg once weekly. This once-weekly regimen is proposed to maintain response while providing time off from pathway inhibition, which may reduce the frequency of AEs. [REDACTED]

[REDACTED] This once-weekly regimen is similar to

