
 
• Diarrhea/colitis (Grade <math>\geq 2</math>)
 
	
Step 1: Interrupt INCB050465. Perform work-up for infection (including CMV, C. difficile, etc). Initiate or continue supportive care (see Section 5.4.2). Consider colonoscopy with biopsy for Grade <math>\geq 3</math>.
 
Step 2: If infection is ruled out, start oral steroids, or consider IV steroids if subject is being given IV fluids. If no improvement with oral steroids, switch to IV steroids.
 
When diarrhea resolves to Grade <math>\leq 1</math>, continue supportive care and taper steroids over 4 weeks. When taper is complete and diarrhea is Grade <math>\leq 1</math>, restart INCB050465 at next lower dose with approval of the medical monitor.
 
If Grade <math>\geq 2</math> diarrhea reoccurs, permanently discontinue INCB050465.

 
• Pneumonitis (Grade 1)
 
	
Step 1: Interrupt INCB050465 until the toxicity has resolved.
 
Step 2: Restart INCB050465 at next lower dose. Monitor as clinically indicated.

 
• Pneumonitis (Grade <math>\geq 2</math>)
 
	
Permanently discontinue INCB050465.

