**Table 2: Guidelines for Interruption and Restarting Study Drug (Continued)**

ADVERSE EVENT	ACTION TAKEN

 
• Skin toxicity (eg, rash, pruritus, etc, unless otherwise specified) (Grade 2-3)
 
	
Step 1: Interrupt INCB050465 until the toxicity has resolved to <math>\leq</math> Grade 1.
 
Step 2: Restart INCB050465 at same dose. If assessed as related to INCB050465, restart at next lower dose.

 
• Exfoliative dermatitis (Grade 1)
 
	
Step 1: Interrupt INCB050465 until the toxicity has resolved.
 
Step 2: Restart INCB050465 at next lower dose. Monitor as clinically indicated.

 
• Exfoliative dermatitis (<math>\geq</math> Grade 2)
 
	Permanently discontinue INCB050465.

 
• Intestinal perforation (any grade)
 
	Permanently discontinue INCB050465.

 
• Pneumocystis jiroveci pneumonia infection
 
	Interrupt INCB050465. Permanently discontinue INCB050465 if Pneumocystis jiroveci pneumonia infection is confirmed.

 
• CMV infection
 
	Subjects with CMV viremia without associated clinical signs of CMV infection should be carefully monitored. Consider interrupting INCB050465 for subjects with CMV viremia and clinical signs of infection until the infection has resolved. Restart INCB050465 reduced by 1 dose level if approved by the medical monitor.

 
• Varicella zoster infection
 
	Interrupt INCB050465. Restart INCB050465 only by approval of the medical monitor.

 
• Any Grade 1 or Grade 2 toxicity unless otherwise specified.
 
	Continue study treatment and treat the toxicity; monitor as clinically indicated.

 
• Any Grade 3 toxicity, if clinically significant and not manageable by supportive care unless otherwise specified.
 
	
Step 1: Interrupt INCB050465 up to 14 days until the toxicity has resolved to <math>\leq</math> Grade 1.
 
Step 2: Restart INCB050465 at same dose. If assessed as related to INCB050465, restart at next lower dose. If interrupted for <math>></math> 14 days, contact the medical monitor for approval to restart INCB050465. Monitor as clinically indicated.

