#### **5.4.3. Definition for Immune-Related Adverse Events**

Adverse events of a potential immunologic etiology, or immune-related AEs (irAEs), may be defined as an AE consistent with an immune phenomenon associated with study drug exposure after all other etiologies have been eliminated. Immune-related AEs may be expected based on previous experience with INCB050465 and other drugs (eg, idelalisib) that inhibit PI3K $\delta$ . Special attention should be paid to AEs that may be suggestive of potential irAEs. Based on emerging data from the ongoing Study INCB 50465-101, most irAEs occur after the first 9 weeks of study drug administration. However, an irAE could occur at any time. Suspected irAEs should be discussed with the medical monitor when possible.

Subjects should receive appropriate supportive care measures as deemed necessary by the treating investigator. Suggested supportive care measures for the management of drug-related AEs with potential immunologic etiology are outlined in Table 2 and Section 5.4.2. For each AE, attempts should be made to rule out other causes, including but not limited to metastatic disease or bacterial or viral infection, which might require specific supportive care.

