8.2.2. Adverse Events of Special Interest or Adverse Events of Clinical Interest

Specific AEs, or groups of AEs, will be followed as part of standard safety monitoring activities.

- ALT \geq 5 × ULN
- AST \geq 5 × ULN
- Colitis
- Diarrhea > Grade 2
- Rash \geq Grade 2
- Intestinal perforation
- Pneumonitis
- Pneumocystis jirovecii infection
- CMV infection
- Herpes simplex virus infection
- Varicella zoster virus infection
- Exfoliative dermatitis

The number of subjects who experienced any TEAEs of special interest will be summarized by maximum severity. Time to onset of new or worsening Grade 3 or 4 AEs will be summarized for ALT, AST, neutropenia, colitis, intestinal perforation, pneumonitis, *Pneumocystis jirovecii* infection, CMV infection, herpes simplex virus infection, varicella zoster virus infection, and exfoliative dermatitis. For rash and diarrhea events, time to onset of new or worsening Grade 2 or higher AEs will be summarized. ALT, AST, and neutropenia will be summarized based on the laboratory data.

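### Time to onset of colitis, pneumonitis and exfoliative dermatitis is summarized only from Grade 3, although Protocol Table 2 interrupts or stops drug at Grade 2 and the SAP times diarrhea and rash from Grade 2

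*SAP*

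**What the plan says.** SAP 8.2.2 plans two outputs for adverse events of special interest.

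- **Counts (Table 3.2.16).** "The number of subjects who experienced any TEAEs of special interest will be summarized by maximum severity". Colitis, pneumonitis and exfoliative dermatitis are listed there without a grade floor.
- **Time to onset (Table 3.2.17).** "Time to onset of new or worsening Grade 3 or 4 AEs will be summarized for ALT, AST, neutropenia, colitis, intestinal perforation, pneumonitis". The list goes on to end with "herpes simplex virus infection, varicella zoster virus infection, and exfoliative dermatitis". The next sentence sets a lower floor for two other terms: "For rash and diarrhea events, time to onset of new or worsening Grade 2 or higher AEs will be summarized".

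Protocol Table 2 acts earlier on the three terms. At Grade 2 or higher exfoliative dermatitis the action is "Permanently discontinue INCB050465", and the row for Grade 2 or higher pneumonitis gives the same instruction. Diarrhea and colitis share one row. At Grade 2 or higher, drug is interrupted and may be restarted at a lower dose after resolution; if Grade 2 or higher diarrhea recurs, the instruction is to "permanently discontinue INCB050465".

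The Protocol also says why timing is of interest. Section 5.4.3 reports from the ongoing first study that "most irAEs occur after the first 9 weeks of study drug administration". Section 1.4 gives the reason for the step-down after 8 weeks: "This once-weekly regimen is proposed to maintain response while providing time off from pathway inhibition, which may reduce the frequency of AEs".

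**The concern.** The onset summary starts its clock above the grade at which the Protocol requires drug to be interrupted or stopped for these terms. A subject taken off treatment for Grade 2 pneumonitis supplies no onset time for pneumonitis. The floor also differs between terms for no stated reason. Protocol 8.4 lists colitis, pneumonitis and exfoliative dermatitis as special-interest events at any grade, and diarrhea and rash only from Grade 2. The onset summary reverses that order, with the lower floor for diarrhea and rash.

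At stake is a descriptive safety result that readers of this trial will look for: when the events that interrupt or end treatment begin, relative to the change from daily to weekly dosing. No efficacy result depends on it.

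**Working it through.** **1. The Protocol's own figures on timing.** Sections 1.3 and 1.4 report that 11 of 46 subjects in Study INCB 50465-101 stopped for an adverse event, and 7 of 20 among responders. 11/46 = 23.9% and 7/20 = 35.0%, matching the stated 24% and 35%. Colitis, pneumonitis and exfoliative dermatitis are among the named causes, and all but 1 of the events came after the 9-week assessment. The grades of these events are not given.

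**2. The two documents side by side.**

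| Term | Lowest grade timed (SAP 8.2.2) | Table 2 at Grade 1 | Table 2 at Grade 2 |
|---|---|---|---|
| Pneumonitis | 3 | interrupt, then lower dose | permanent stop |
| Exfoliative dermatitis | 3 | interrupt, then lower dose | permanent stop |
| Colitis | 3 | treat; move to the Grade 2 guidance if no better after 48 hours | interrupt, then lower dose |
| Diarrhea | 2 | same row as colitis | same row as colitis; permanent stop on recurrence |
| Rash | 2 | continue (general Grade 1 rule) | interrupt |

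For diarrhea and rash, the lowest grade timed is the grade at which Table 2 first interrupts drug. For the other three terms it lies above that grade, and for pneumonitis and exfoliative dermatitis it also lies above the grade of the mandatory stop.

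**3. What follows for Table 3.2.17.**

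- A subject whose worst grade is 2 for one of the three terms contributes no onset time for that term.
- Protocol 8.1.2 records each change in severity as a separate event with its own start date. A Grade 2 event that reaches Grade 3 therefore enters at the date of worsening. Under Protocol Table 3 the planned switch is Week 9, Day 1, that is Day 8 × 7 + 1 = 57. An event that begins in Week 8 and reaches Grade 3 in Week 9 would be timed after the planned switch although it began before it.
- One Grade 2 bowel event enters the summary if coded as diarrhea and not if coded as colitis, although Table 2 manages both in one row.

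**4. What is still reported.** Table 3.2.16 counts these events by highest grade. Tables 3.2.18 and 3.2.24 to 3.2.26 give events on the weekly schedule, and those leading to reduction, interruption or discontinuation, by system organ class and preferred term with no grade floor. They show that an event fell in the weekly period. They do not show when it began, and the discontinuation table is not split by grade.

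**5. Scale.** The omitted share cannot be computed, because neither document gives a grade split. For illustration only, assume 10 subjects whose worst grade is 2 or higher for one of these terms, and let *s* be the share whose worst grade is exactly 2. Onset times omitted = 10 × *s*; still counted = 10 × (1 − *s*).

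| *s* (assumed) | Omitted | Counted |
|---|---|---|
| 25% | 2.5 | 7.5 |
| 50% | 5 | 5 |
| 75% | 7.5 | 2.5 |

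**The case against.** The strongest defense is that the report does not lose these events. A Grade 2 pneumonitis that ends treatment on weekly dosing appears in Tables 3.2.16, 3.2.18 and 3.2.26. The stated aim of the weekly schedule is to lower the frequency of adverse events, and frequency is covered at all grades. The first study's timing was itself reported as before or after the 9-week assessment, and the weekly-schedule tables split at nearly the same point. The trial is single-arm with descriptive safety analyses, so onset times could not show that the schedule reduced anything. Table 2 already acts at Grade 1 for pneumonitis and exfoliative dermatitis, so Grade 2 is not the only defensible floor.

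Most of this stands, and it limits the point in three ways where a reader might infer more.

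- *That the plan misses the events the weekly schedule was meant to reduce.* It does not. Grade 3-4 events are timed, lower grades are counted, and nothing shows what grades the first study's discontinuing events had.
- *That Table 3.2.17 is the only planned information on timing.* It is the only time-to-onset summary, but the weekly-schedule tables also place events before or after the switch.
- *That the onset times are biased toward early values because subjects leave for progression.* SAP 8.2.2 names no estimator and the table shells are in a separate document, so this cannot be shown. The dating of worsened events works in the opposite direction.

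The defense does not explain the different floors. It gives no reason to time Grade 2 diarrhea but not Grade 2 colitis, or to give no onset time to a Grade 2 event that ends treatment.

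**Conclusion.** The point holds as a narrow inconsistency in one descriptive safety summary. Grade 2 colitis, pneumonitis and exfoliative dermatitis have no summarized onset time, including events that end treatment; worsened events are dated at the worsening; and bowel events are handled differently by coded term. These conclusions follow from the text of SAP 8.2.2, Protocol Table 2 and Protocol 8.1.2 and need no assumption.

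The size in numbers of events is unknown. The range of 2.5 to 7.5 omitted per 10 rests wholly on the assumed 25% to 75% share and should not be quoted as an estimate. Event counts, the primary endpoint and the secondary efficacy endpoints are unaffected. The case for a change is that it is cheap and that the Protocol's dosing rationale refers to when such events occur.

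**What to change.** In SAP 8.2.2 and Table 3.2.17, add time to first onset at Grade 2 or higher for pneumonitis, exfoliative dermatitis and colitis. Show colitis also combined with diarrhea, so that the result does not depend on the coded term. Date each from the first record at Grade 2 or higher, and keep the Grade 3-4 rows beside the new ones.

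The graded start dates are already collected under Protocol 8.1.2. One footnote is needed: after Amendment 4, Protocol 7.4.1 narrows the required CRF recording to serious events and those leading to discontinuation, so a later Grade 2 colitis that only interrupts drug may not be captured there.

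The cost is SAP wording and a few extra rows in one table. No clinical rule in Table 2 changes. A cumulative-incidence analysis with competing events would be an optional refinement and is not needed to settle this point.

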8.2.3. Adverse Event Summaries

An overall summary of AEs will include:

- Number (%) of subjects reporting any TEAEs
- Number (%) of subjects reporting any SAEs
- Number (%) of subjects reporting any Grade 3 or 4 TEAEs
- Number (%) of subjects reporting any TEAEs related to INCB050465
- Number (%) of subjects reporting any SAEs related to INCB050465
- Number (%) of subjects reporting any Grade 3 or 4 AEs related to INCB050465
- Number (%) of subjects who temporarily interrupted INCB050465 because of TEAEs
- Number (%) of subjects who permanently discontinued INCB050465 because of TEAEs
- Number (%) of subjects with INCB050465 dose reductions because of TEAEs

- Number (%) of subjects who had a fatal TEAE
- Number (%) of subjects reporting any TEAEs during QW schedule
- Number (%) of subjects reporting any SAEs during QW schedule
- Number (%) of subjects reporting any Grade 3 or 4 TEAEs during QW schedule
- Number (%) of subjects reporting any TEAEs related to INCB050465 during QW schedule
- Number (%) of subjects who temporarily interrupted INCB050465 because of TEAEs during QW schedule
- Number (%) of subjects who permanently discontinued INCB050465 because of TEAEs during QW schedule
- Number (%) of subjects with INCB050465 dose reductions because of TEAEs during QW schedule
- Number (%) of subjects who had a fatal TEAE during QW schedule

The following summaries will be produced by MedDRA term (if 10 or fewer subjects appear in a table, a listing may be appropriate):

- Summary of TEAEs by SOC and PT
- Summary of TEAEs by PT in decreasing order of frequency
- Summary of TEAEs by SOC, PT, and maximum severity
- Summary of Grade 3 or 4 TEAEs by SOC and PT
- Summary of INCB050465 treatment-related AEs by SOC and PT
- Summary of INCB050465 treatment-related AEs by SOC, PT, and maximum severity
- Summary of Grade 3 or 4 INCB050465 treatment-related AEs by SOC and PT
- Summary of TEAEs leading to death by SOC and PT
- Summary of treatment-emergent SAEs by SOC and PT
- Summary of treatment-emergent SAEs by PT in decreasing order of frequency
- Summary of INCB050465 treatment-related SAEs by SOC and PT
- Summary of TEAEs leading to INCB050465 dose reduction by SOC and PT
- Summary of TEAEs leading to INCB050465 dose interruption by SOC and PT
- Summary of TEAEs leading to discontinuation of INCB050465 by SOC and PT
- Summary of TEAEs during QW schedule by SOC and PT
- Summary of Grade 3 or 4 TEAEs during QW schedule by SOC and PT
- Summary of INCB050465 treatment-related AEs during QW schedule by SOC and PT

- Summary of TEAEs leading to death during QW schedule by SOC and PT
- Summary of treatment-emergent SAEs during QW schedule by SOC and PT
- Summary of INCB050465 treatment-related SAEs by SOC and PT
- Summary of TEAEs leading to INCB050465 dose reduction during QW schedule by SOC and PT
- Summary of TEAEs leading to INCB050465 dose interruption during QW schedule by SOC and PT
- Summary of TEAEs leading to discontinuation of INCB050465 during QW schedule by SOC and PT

8.3. Clinical Laboratory Tests

8.3.1. Laboratory Value Definitions

Laboratory values and change from baseline values will be summarized descriptively by visit. Baseline will be determined according to Section 4.1.3. If there are multiple values that meet the criteria for baseline, the value from the central laboratory has priority over the value from the local laboratory. Thereafter, additional rules may be provided after consultation with the medical monitor to delineate which value will be defined as baseline.

Laboratory test values outside the normal range will be assessed for severity based on CTCAE grade or similar criteria where clinical intervention is required for CTCAE grading. The incidence of abnormal laboratory values and shift tables relative to baseline will be tabulated.

8.3.2. Laboratory Value Summaries

All test results and associated normal ranges from central laboratories will be reported in SI units. Any laboratory test results and associated normal ranges from local laboratories will be converted to SI units.

When there are multiple laboratory nonmissing values for a subject's particular test at a scheduled visit, central laboratory values have higher priority over local laboratory values. If a tie still exists, the laboratory value with the smallest laboratory sequence number will be used in by-visit summaries.

Numeric laboratory values will be summarized descriptively in SI units, and non-numeric test values will be tabulated when necessary. In addition, line graphs will be provided for hemoglobin, platelet counts, WBC, neutrophils, and lymphocytes.

Shift tables will be presented showing change in CTCAE grade from baseline to worst grade postbaseline. Separate summaries for abnormally high and abnormally low laboratory values will be provided when the laboratory parameter has both high and low grading criteria. The denominator for the percentage calculation will be the number of subjects in the baseline category.

8.4. Vital Signs

Values at each scheduled visit, change, and percentage change from baseline for vital signs, including weight, systolic blood pressure, diastolic blood pressure, pulse, respiratory rate, and body temperature will be summarized descriptively.

Criteria for clinically notable vital sign abnormalities are defined in Table 2. The abnormal values for subjects exhibiting clinically notable vital sign abnormalities will be listed along with their assigned treatment group. Alert vital signs are defined as an absolute value outside the defined range and percentage change greater than 25%. The abnormal values for subjects exhibiting alert vital sign abnormalities will be listed.

Table 2: Criteria for Cl	linically Notable Vi	ital Sign Abnormalities
--------------------------	----------------------	-------------------------

Parameter	High Threshold	Low Threshold	
Systolic blood pressure	> 155 mmHg	< 85 mmHg	
Diastolic blood pressure	> 100 mmHg	< 40 mmHg	
Pulse	> 100 bpm	< 45 bpm	
Temperature	> 38°C	< 35°C	
Respiratory rate	> 24/min	< 12/min	

8.5. Electrocardiograms

Twelve-lead ECGs including PR, QRS, QT, QTcF, and RR intervals will be obtained for each subject during the study. Values at each scheduled visit, change, and percentage change from baseline will be summarized for each ECG parameter. Baseline will be determined as the average of all nonmissing values before the first administration of INCB050465.

Normal ranges for ECG values are defined in Table 3. Electrocardiogram values will be considered abnormal as well if the absolute percentage change from baseline is more than 25% (30% for QRS interval). Subjects exhibiting ECG values outside the normal ranges will be listed with study visit and assigned treatment group. Abnormal values for subjects with alert ECG values, defined as both the absolute value and the percentage change from baseline being outside normal ranges, will be identified and listed. Outliers of QT and QTcF values, defined as absolute values > 450 msec or change from baseline > 30 msec, will be summarized.

Table 3: Normal Ranges for Electrocardiogram Values

Parameter	High Threshold	Low Threshold
QTcF	> 460 msec	< 295 msec
PR	> 220 msec	< 75 msec
QRS	> 120 msec	< 50 msec
QT	> 500 msec	< 300 msec
RR	> 1330 msec	< 600 msec

QTcF = Fridericia's correction.

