### **7.4.4. Twelve-lead Electrocardiograms**

All 12-lead ECGs will be performed with the subject in a recumbent or semirecumbent position after 5 minutes of rest. Baseline ECGs will be obtained during screening using a single measurement, but can be done in triplicate if the single QTc measurement is > 450 milliseconds (corrected by Fridericia; see Section 3.2). Electrocardiograms will also be obtained during the Day 1 visit (triplicate measurements) before the subject receives the first dose of study drug. Triplicate ECGs will be performed predose and 1.5 hours ( $\pm$  15 minutes) after receiving INCB050465 on Day 15. When triplicate ECGs are being obtained, individual measurements should be performed 5 minutes ( $\pm$  3 minutes) apart. All 12-lead ECGs obtained at subsequent timepoints (single measurements) will be compared with the baseline 12-lead ECGs as follows:

- For ECG morphology, all postdose ECG recordings will be compared with Day 1 predose ECGs.
- For the calculation of changes in cardiac intervals (eg, QT interval), the intervals from the screening and Day 1 predose (triplicate) ECGs will be computed and averaged and used as the baseline for comparison of all postdose intervals.

If a single measurement demonstrates a QTc interval > 500 milliseconds, 2 more ECGs should be obtained over a brief period, and the averaged QTc intervals should be used to determine whether the study treatment should be interrupted.

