### **9.4.2.3. Vital Signs**

Descriptive statistics and mean change from baseline will be summarized for vital signs (weight, blood pressure, pulse, respiratory rate, and body temperature) at each assessment time. Vital sign results will be reviewed for clinically notable abnormalities (see [Table 12](#)), and subjects

exhibiting clinically notable vital sign abnormalities will be listed. A value will also be considered an "alert" value if it is outside the established range and shows a > 25% change from baseline. The abnormal values for subjects exhibiting alert vital sign abnormalities will be listed

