**9.4.2.4. Electrocardiograms**

Descriptive statistics and mean change from baseline will be summarized for the ECG parameter at each assessment time. Average of all values before the first dose of study drug will be used as the baseline value. Criteria for clinically notable ECG abnormalities are defined (see Table 13). The abnormal values for subjects exhibiting clinically notable ECG abnormalities will be listed. Alert ECG values are defined as an absolute value outside the defined range and absolute percentage change > 25% (30% for QRS) interval. The abnormal values for subjects exhibiting alert ECG abnormalities will be listed. Outliers of QT, QTcB, and QTcF, defined as absolute values > 450 milliseconds or change from baseline > 30 milliseconds, will also be listed.

[figure not shown]

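### The 25% change condition makes the temperature alert unreachable and leaves some QTcF values above 500 ms out of the ECG alert listing

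*SAP*

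**What the plan says.** **ECG.** Protocol 9.4.2.4 states: "Alert ECG values are defined as an absolute value outside the defined range and absolute percentage change > 25% (30% for QRS) interval". SAP 8.5 has the same two-part rule: "alert ECG values, defined as both the absolute value and the percentage change from baseline being outside normal ranges". The percentage limit comes from the preceding text of SAP 8.5: "absolute percentage change from baseline is more than 25% (30% for QRS interval". SAP Table 3 sets the QTcF upper limit at 460 ms.

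**Vital signs.** SAP 8.4 states: "Alert vital signs are defined as an absolute value outside the defined range and percentage change greater than 25" percent. Protocol 9.4.2.3 likewise calls a value an alert "if it is outside the established range and shows a > 25% change from baseline". SAP Table 2 gives temperature limits of 38 °C (high) and 35 °C (low). Neither vital-signs section says that the percentage change is absolute; the ECG sections do.

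**Other displays.** SAP 8.4 and 8.5 also list every out-of-range vital sign and ECG value with no percentage condition (Listings 2.9.2 and 2.10.2 in Appendix A). SAP 8.5 further summarizes "Outliers of QT and QTcF values, defined as absolute values > 450 msec or change from baseline > 30 msec" (Table 3.5.6).

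**Conduct.** Protocol 7.4.4 has its own step at a higher level: "If a single measurement demonstrates a QTc interval > 500 milliseconds, 2 more ECGs should be obtained over a brief period". The averaged QTc then informs whether treatment is interrupted.

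**The concern.** One percentage limit is applied to parameters that vary on very different relative scales. A 25% change may be a workable screen for pulse or blood pressure. For body temperature in °C, 25% lies far outside any reading a patient will have. For QTcF, 25% of an ordinary baseline is about 100 ms or more.

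Two things are at stake, both in safety display:

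- A temperature alert test that cannot be met carries no information, whatever happens in the trial. Temperature matters here: Protocol 1.5 names infections and fever among the potential risks, and Protocol 1.3 reports fever among the adverse events seen in at least 20% of subjects in the earlier study.
- The protocol's own QTc action level and the QTcF alert listing do not line up. The only planned QT/QTcF outlier summary starts at 450 ms, which is also the screening limit, so it pools a value of 455 ms with one of 520 ms.

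**Working it through.** The documents give no figure to reproduce here, so the rule is applied directly.

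**Inputs**
- Percentage limit: 25% for temperature (SAP 8.4) and QTcF (SAP 8.5).
- Range limits: temperature above 38 or below 35 °C (SAP Table 2); QTcF above 460 ms (SAP Table 3).
- QTc screening limit: 450 ms, Fridericia (Protocol 3.2, exclusion 18).
- ECG baseline: mean of all nonmissing predose values (SAP 8.5).
- Assumption: temperature baselines of 35 to 38 °C, which is the Table 2 range, and readings of about 30 to 43 °C. The documents state no physiological limits.

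**Formula.** With baseline *b*, a high alert needs a value above max(upper limit, 1.25 × *b*). A low alert needs a value below min(lower limit, 0.75 × *b*), if the change is read as absolute.

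**Temperature**

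| Baseline (°C) | High alert above (°C) | Low alert below (°C) |
|---|---|---|
| 35 | 43.75 | 26.25 |
| 36 | 45.0 | 27.0 |
| 37 | 46.25 | 27.75 |
| 38 | 47.5 | 28.5 |

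Working backwards, an alert at 41 °C would need a baseline below 41 / 1.25 = 32.8 °C. No reading in the assumed range meets either limit. If the change in SAP 8.4 is read as signed, a fall can never be flagged for any vital sign.

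**QTcF.** The cut-off is max(460, 1.25 × *b*). The values above 500 ms that are not flagged run from just over 500 ms up to 1.25 × *b*.

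| Baseline (ms) | Alert above (ms) | Unflagged band above 500 ms (width, ms) |
|---|---|---|
| 380 | 475 | none |
| 400 | 500 | none |
| 401 | 501.25 | 1.25 |
| 420 | 525 | 25 |
| 440 | 550 | 50 |
| 450 | 562.5 | 62.5 |
| 460 | 575 | 75 |

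At exactly 400 ms nothing above 500 ms is missed: 501 ms is a change of 101 / 400 = 25.25% and is flagged. The gap opens strictly above 400 ms. The 450 ms limit applies at screening, while the analysis baseline also averages Day 1 values, so a baseline slightly above 450 ms is possible. The 460 ms row shows the effect.

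**Example.** A rise from 420 to 510 ms is +90 ms, or 90 / 420 = 21.4%, so it is not an alert. It is above 460 ms, so it appears in Listing 2.10.2. It is above 450 ms and its change exceeds 30 ms, so it meets both criteria for Table 3.5.6. Within that table's definition nothing distinguishes it from a value of 455 ms.

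**The case against.** The strongest reply is that the alert listings are a subset of wider displays and nothing is hidden. This stands. Every temperature above 38 °C is in Listing 2.9.2, every QTcF above 460 ms is in Listing 2.10.2, and all values are in Listings 2.9.1 and 2.10.1. With at most 120 subjects, QTcF values above 500 ms can be read off the abnormal listing by eye.

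It also stands that patient safety does not depend on these listings. The 500 ms step in Protocol 7.4.4 is carried out at the site, and that section adds central flagging and medical monitor review of clinically significant abnormal ECGs. Under Protocol 7.4.3, clinically significant vital-sign abnormalities are reported as adverse events, so an important fever reaches the adverse event tables.

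A reader might infer more: that the alert listings fail to show the very values they were created for, or that the report would look clean for fever and QTc prolongation. The documents do not support this. They never state the purpose of the alert listings, and the abnormal listings and Table 3.5.6 belong to the same planned output. Nor does the rule miss QTcF above 500 ms as a class, since anything above 1.25 times baseline is flagged.

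What the reply does not answer is that the SAP states a test for temperature that cannot be met, and that no summary it defines uses the protocol's own 500 ms level.

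**Conclusion.** The point holds as a minor but real weakness in two safety listings and one summary table. The temperature alert is empty in practice. For QTcF, the alert listing leaves out a baseline-dependent band above 500 ms that reaches 62.5 ms at the screening limit.

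The temperature conclusion rests on the assumed range of baselines and readings, but the margin is wide: even the lowest high cut-off, 43.75 °C, is above that range. The QTcF conclusion is arithmetic and needs only a baseline above 400 ms, which the eligibility criteria allow. How many subjects would fall in the band cannot be judged from the documents.

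The statement about Table 3.5.6 rests on its definition in SAP 8.5. Appendix A marks it as a standard table whose layout is held elsewhere, so a finer split there cannot be excluded. The SAP and Protocol agree on the two-part rule, so this is a matter of how the rule is built and not a conflict between the documents.

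**What to change.** **SAP 8.5.** Flag any QTcF above 500 ms as an alert whatever the percentage change, keeping the existing rule for the other ECG parameters. Report a separate category above 500 ms in Table 3.5.6. This uses the level already in Protocol 7.4.4 and changes only the display. Finer categories, such as 480 ms or a change of more than 60 ms, are optional and have no source in the documents.

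**SAP 8.4.** Replace the percentage test for temperature with a prespecified absolute change, or state that the alert test does not apply to temperature and refer the reader to Listing 2.9.2. For the remaining vital signs, say that the percentage change is absolute, as SAP 8.5 does.

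Because Protocol 9.4.2.3 and 9.4.2.4 carry the same rule, record the departure in SAP 10.1.

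**Cost.** A few lines of SAP text, minor programming and slightly longer listings. No new data are needed.
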